The figure shows 2 Dog-leg phases each with 3 randomisation sequences. In the first, 48 hospitals (clusters) are ready to recruit and these are randomised between the 3 sequences. All 3 sequences are eventually exposed to the intervention. Sequence 1 immediately receives the training intervention and data are only collected after the intervention. In sequence 2, data are collected before and after the intervention. The final sequence collects data only before the intervention. The second dogleg commences after the first when more clusters are ready to participate (this is shown as one month on the figure, but can be delayed as practicable). Indicatively, 7 dogleg phases with 48 hospitals (336 hospitals total) each will achieve the sample size required (333 clusters). The timeline for the middle sequence (sequence 2) is shown below. The event rate will be monitored by the DMOC and the sample size reviewed after 50 centres have completed the baseline recruitment.

[figure not shown]

Figure 2: Timeline for site and patient participation

Cluster randomisation

Randomisation of hospitals will be conducted in phases. Within a phase, the available hospitals will be organised into matched triplets according to hospital size (total number of hospital beds) and World Bank country income classification (low, lower middle, upper middle, high income), and whether the hospital accepts referrals from surgeons from at other hospitals of patients needing right colectomy. Within each matched triplet, each hospital will be randomised to a different sequence (three possible randomised sequences).

Co-enrolment

EAGLE permit co-enrolments into other research studies, so long as the study intervention does is not evaluating technical or perioperative interventions where anastomotic leak is the primary outcome measure. The Data Monitoring Oversight Committee (DMOC) will monitor baseline anastomotic leak rates throughout the study period.

ELIGIBILITY

Hospital inclusion criteria

Any hospital or surgical unit performing elective and/or emergency colorectal surgery. There are no restrictions for hospital/unit size or case volume.

Patient inclusion criteria

- All adult patients (age 18 years and above) undergoing right colectomy with or without primary anastomosis. Right colectomy is defined as ileocaecal resection or right hemicolectomy (any colonic transection with the distal resection margin proximal to the splenic flexure).

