These four core components are considered mandatory, but adjustment of the checklist to fit into the flow of care at each included centre if permitted. A paper copy of the Safe-anastomosis checklist should be completed and inserted into each participants clinical notes.

3. Harmonised technique for stapled and handsewn anastomosis

A two stage Delphi exercise was undertaken by over 200 specialist colorectal surgeons from around Europe. This has enabled the development of harmonising guidance for surgeons in the absence of high-quality evidence. Such guidance can be amended as new data becomes available. This data has been incorporated into the training platform.

Training platform

The training platform for the study intervention is the ESCP Safe-anastomosis Online Educational Module. This is a secure, password protected Electronic Learning Management System which houses a five-modular educational platform.

- (1) **Decision making**, including a pre-operative risk stratification tool for anastomotic leak
- (2) **ESCP Safe-anastomosis checklist**, including components and implementation within a theatre team
- (3) **Preparing for anastomosis**, including anastomotic healing bowel preparation, choice of stapled versus handsewn anastomoses
- (4) **Stapled anastomosis**, including harmonising technique and checking for technical failure.
- (5) **Handsewn anastomosis**, including harmonising technique, common variations and checking for technical failure.

It is intended that this educational module should be completed by any providers of colorectal surgical procedures (including consultant/attending surgeons, trainee/resident surgeons, and surgical care practitioners/allied healthcare professionals in surgery) in the one-month implementation period.

A dedicated implementation pack for theatre teams (anaesthetists, scrub nurses, operating theatre practitioners) including an abridged Microsoft PowerPoint Slide set (with translation), Animated video, and in-theatre posters will also be provided. These 'ESCP Safe-anastomosis Theatre Teams' packs will be available across several languages.

VALIDATION OF LEARNING PLATFORM

The training program has been reviewed by the ESCP Education Committee (Chair: [name]) and revised. It has also been reviewed by the independent Study Steering Committee (Chair: [name]). The platform has been used by 20 international surgeons to ensure language and clarity of meaning is not lost across different cultures.

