STATISTICAL ANALYSIS PLAN

This will be conducted on an intention-to-treat basis i.e. all patients recorded in the database during the scheduled 2-month recruitment periods will be included, and those in the second period will be considered exposed to the intervention regardless of whether learning from the intervention was actually implemented. The primary outcome will be 30-day anastomotic leak rate. In the primary analysis, 30-day leak rate will be modelled using mixed effects logistic regression with random cluster (hospital) effects allowing inclusion of baseline risk factors such as co-morbid disease and ASA score and adjustment for a fixed time effect between time periods.

Planned additional analyses

Pre-planned exploratory sub-group analyses of the primary outcome will be performed in the following groups:

At cluster (hospital) level:

- Number of beds (<500 versus ≥500 total hospital beds).
- Right colectomy volume (<10 patients versus ≥10 patients per 2 month period).
- Early adoption (early versus late study entrants).
- Health service expenditure per capita in purchasing parity (top versus middle versus bottom tertile).
- Proportion of operating surgeons in each centre completing the online training modules prior to 'post-implementation' data collection (high [≥80%], intermediate [50-79%], low [<50%]).
- World Bank income group (high versus middle/low income country).

At patient level:

- Indication for surgery (malignant versus benign, e.g. inflammatory bowel disease).
- Procedure urgency (elective versus expedited/ emergency).
- Age (≤65 years versus >65 years).
- Operative approach (open versus laparoscopic/ robotic).
- Anastomotic technique (stapled versus handsewn anastomosis).
- Primary operating surgeon experience as reported (trainee versus consultant).
- Primary operating surgeon specialism as reported (general versus colorectal surgeon).

Reverse analysis will also be undertaken to explore what are the characteristics of hospitals with a big change versus no change, and do these differ in respect of cluster characteristics.

DATA HANDLING AND RECORD KEEPING

Source Data

Source data within the EAGLE study will be kept as part of the participants' medical notes generated and maintained at site. As all data collected and analysed within the EAGLE study are routinely collected, source data will only be within the medical notes.

Data Management

Information will be collected at the following times:

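### The exploratory comparison of big-change and no-change hospitals sorts one third of hospitals mostly by chance and volume; the training-completion and technique subgroups need a clearer definition and label

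*Protocol*

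**What the plan says.** The Protocol's section Planned additional analyses lists exploratory subgroups of the primary outcome at hospital and patient level. It then adds: "Reverse analysis will also be undertaken to explore what are the characteristics of hospitals with a big change versus no change", and asks whether such hospitals differ in their cluster characteristics. It does not define a big change or limit the analysis to particular sequences.

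The text to Figure 1 (Study Design) fixes which hospitals have which data. Hospitals in sequence 1 are trained at once and contribute post-training patients alone. The middle group is the only one with two periods: "In sequence 2, data are collected before and after the intervention". Hospitals in sequence 3 contribute pre-training patients alone, although they too are trained later.

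Under Cluster randomisation, allocation is equal: "Within each matched triplet, each hospital will be randomised to a different sequence (three possible randomised sequences").

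Two of the listed subgroups bear on the same issue. One hospital-level subgroup is "Proportion of operating surgeons in each centre completing the online training modules prior to" the start of post-implementation data collection, in three bands. One patient-level subgroup is "Anastomotic technique (stapled versus handsewn anastomosis"). The Training platform section says that the third educational module includes the "choice of stapled versus handsewn anastomoses".

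**The concern.** A before-after change cannot be observed in a hospital that contributes only one period. That excludes sequences 1 and 3 from any grouping by observed change. In sequence 2, each period is expected to yield less than one leak per hospital, so one leak more or fewer decides the group. Characteristics found to separate the groups could then be published as explaining who benefits when they mainly reflect chance and case volume.

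The two subgroups raise different issues:

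- **Training completion.** It is a measure of uptake taken after randomisation, and as worded it has no reference point in sequence 3. It is also the subgroup most easily read as a dose-response.
- **Technique.** It is chosen during the operation, after the team may have been trained on that choice. The stapled and handsewn strata may therefore hold different patients with and without the intervention.

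**Working it through.** **Inputs (Protocol, Sample Size).** Leak rate p1 = 0.081 falling to p2 = 0.056; 80% power; 5% significance (two-sided assumed, as sidedness is not stated); ICC 0.05 without decay; m = 10 patients per hospital per 2-month period. Only patients with a primary anastomosis enter the primary denominator, so 10 is an upper figure for the average.

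**1. The plan's own sample size.** Two proportions with individual randomisation need 1,602 per arm, 3,204 in all. A generalised least squares variance for the three-sequence layout, with fixed period effects and a random hospital effect, gives a design effect of 1.20.

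- Patients: 3,204 × 1.20 = 3,845.
- Each triplet supplies 10 + 20 + 10 = 40 patients, so clusters = 3,845 / 40 × 3 = 288.
- The Protocol states 3,895 and 292, within 1.3%. The layout used here is therefore the planned one.

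**2. Who has which data.** 333 / 3 = 111 hospitals per sequence.

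- Hospitals with a before-after pair: 111. Without: 222.
- Control patients: 111 × 10 (sequence 2, before) + 111 × 10 (sequence 3) = 2,220. Sequence 3 supplies 1,110 of these, or half.

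**3. Precision of one hospital's change.** Expected leaks are 10 × 0.081 = 0.81 before and 10 × 0.056 = 0.56 after. With no decay in the ICC the hospital effect cancels in the difference:

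SD = √{[p1(1−p1) + p2(1−p2)](1−ICC)/m} = √{(0.0744 + 0.0529) × 0.95 / 10} = 0.110

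This is 11.0 points, or 4.4 times the 2.5-point target. Leaving the ICC out gives 11.3. At m = 5 the SD is 15.6 points; at m = 20 it is 7.8.

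**4. How much of the observed variation could be real.** The Protocol gives no between-hospital SD (τ) of true effects, so a range is assumed. The real share is τ²/(τ² + SD²) at m = 10:

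| τ (points) | Real share |
|---|---|
| 1.25 | 1.3% |
| 2.5 | 4.9% |
| 5 | 17% |

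For 80% reliability at τ = 2.5 points, m = 0.1273 × 0.95 / (0.025² × 0.25) = 774 patients per period per hospital.

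**5. Simulated classification.** Beta-binomial hospitals, mean 8.1%, ICC 0.05, m = 10:

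| Scenario | Fall | No change | Rise |
|---|---|---|---|
| No effect | 28% | 44% | 28% |
| Same relative effect in every hospital | 34% | 47% | 19% |

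In the second scenario no hospital responds differently in relative terms, yet hospitals still spread over all three groups. With no effect, hospitals with no leak at baseline rise by 5.3 points on average, and those with two or more fall by 11.2 points. That is regression to the mean.

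**6. Volume.** The no-effect simulation repeated at other volumes:

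| m per period | Fall of at least 20 points | No change |
|---|---|---|
| 5 | 21% | 58% |
| 10 | 9% | 44% |
| 20 | 2% | 32% |

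Small hospitals thus fill both groups to be compared. Table 1 under Projected Recruitment shows that 19% of audit centres contributed 1-5 patients; there a single leak moves the rate by at least 20 points.

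**7. The two subgroups.** No bias can be computed for either, because the Protocol gives no shift in technique or uptake.

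- Training completion: every hospital implements the programme (Study Design), and centre-level completion is monitored (Safe-anastomosis Champions and Training). A value for sequence 3 can therefore be obtained. The wording simply does not say when it is taken.
- Technique: the training covers the choice, and the checklist reviews the type of anastomosis. The background reports a higher leak risk with stapling and more handsewing in high-risk emergency operations. The split is thus on a prognostic choice that the intervention can alter.

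**The case against.** The strongest reply has five parts.

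- **The reverse analysis is one exploratory sentence.** It names no estimator, cut-off or analysis set, and an unseen SAP could restrict it to sequence 2 or model it differently. That is fair as to detail. But the sentence does fix a comparison of hospitals grouped by change, and restricting it to sequence 2 would leave the 11-point SD untouched. The changing quantity is not named; leak rate is the natural reading and is assumed here.
- **Baseline leak rate is not a listed hospital characteristic.** A reader might infer from the regression to the mean that the trial will report that hospitals with high baseline rates improve most. The Protocol plans no such comparison. For factors unrelated to volume, noise in the grouping would mainly dilute associations. Volume is a listed factor, however, and number of beds may go with it; chance alone separates hospitals on volume.
- **The cluster-level subgroups already cover much of the question.** This stands, and it is a further reason why the reverse analysis is not needed.
- **Post-implementation can be read as the end of the implementation month.** This is a reasonable reading, and one clarifying phrase settles it. A reader might infer that the completion data cannot exist in sequence 3; the Protocol does not support that.
- **Nothing says that the training favours stapling or handsewing.** Correct. Bias in that subgroup is possible, not shown.

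**Conclusion.** The reverse analysis should not be run as described. It can use about 111 of 333 hospitals. In those, an observed change has an SD of about 11 points against a 2.5-point target, and about 28% of hospitals would show a fall with no true effect. This rests on the Protocol's 10 patients per period, 8.1% and 5.6%, and ICC of 0.05. It also holds at 20 patients per period, where the SD is 7.8 points. The share of variation that is real depends on an assumed spread of true effects, but even a 5-point spread gives only 17%.

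A reader might extend the missing two-thirds to all three analyses. It applies only to the reverse analysis: the training category, read literally, lacks a reference point in one third of hospitals, and technique is recorded on every case report form. Nor does the Protocol show that the two subgroups will be biased. Each is open to bias of unknown size. The matter is one of exploratory reporting; the sample size and primary estimate do not depend on it.

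**What to change.** 1. Drop the reverse analysis. Answer its question with exposure-by-hospital-characteristic interactions in the primary mixed logistic model, using all three sequences and reporting estimates with confidence intervals. A random exposure slope may be added, though it will probably be imprecise at this cluster size. The same models serve the cluster-level subgroups already listed.
2. Define training completion at the end of each hospital's own one-month implementation period in every sequence, including sequence 3. Report it as an uptake measure taken after randomisation, not as a randomised dose-response.
3. Label stapled versus handsewn a non-randomised comparison.

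The cost is wording in the analysis plan. Completion is already monitored and every hospital implements the programme, so no new type of data is needed. There is a small downside: completion in sequence 3 is measured later in calendar time, after those hospitals have finished collecting patient data, and uptake there may differ for that reason.

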The study intervention will be introduced at a specific timepoint determined by the randomisation sequence. Sites will not be exposed to the study intervention before their allocated timing and this will be ensured by time-locked password access to QII materials.

Intervention details

The EAGLE Safe-anastomosis Quality Improvement Intervention (QII) is a behavioural change intervention composed of three parts:

1. Routine patient-level stratification of risk of anastomotic leak

Calculation of a preoperative risk for each patient undergoing right colectomy or ileocaecal resection using the anastomoticleak.com risk calculator. This includes six factors: Gender; Body Mass Index >30; Anticoagulant use; Intraoperative complication; Serum protein level; Hospital size. Investigators will be trained and encouraged to preoperatively calculate the risk with or without an intraoperative complication. This risk estimate will be used to inform shared decision

making with the patient preoperatively, and will be reviewed in light of intraoperative events as part of the ECSP Safe-anastomosis Checklist.

2. ESCP Safe-anastomosis Checklist

The ESCP Safe-anastomosis Checklist will be implemented in-theatre, immediately prior to the time of formation of an anastomosis or formation of a stoma; this can be before or after transection of the bowel. The checklist should be completed by an unscrubbed member of the theatre team in partnership with the operating surgeon(s), other members of the surgical team, the scrub nurse(s), anaesthetist(s) and operating department practitioner(s).

The Safe-anastomosis checklist (Appendix 1) consists of:

- (1) Review of any concerns from the anaesthetist, including the anaesthetic risk, haemodynamic instability, vasopressors, blood transfusion, operating time greater than 4 hours, or blood loss greater than 100mls;
- (2) Review of any concerns from the surgical team, including the surgeon, scrub staff and operating theatre practitioners. A consensus decision for primary anastomosis (with or without defunctioning enterostomy) or defunctioning enterostomy without anastomosis will be then made by the operating surgeon.
- (3) If the consensus decision is to proceed with anastomosis; planning equipment, anastomotic configuration, and delivery of an agreed anastomotic technique, including intra-operative checking of anastomosis integrity.

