SAFE-ANASTOMOSIS CHAMPIONS AND TRAINING

The EAGLE study will be led at each site by a surgeon Principal Investigator. This will be a consultant (attending) surgeon who is responsible for the overall conduct of the study. In addition, they will recruit three co-principal investigators who will act as 'Safe-anastomosis champions' in their centre; this will usually include one surgical trainee, one anaesthetic and one theatre nurse. These site champions will oversee dissemination of training to surgeons, trainees, anaesthetists and theatre staff at their site, and sustainability of implementation of the Safe-anastomosis QII. The 'Safe-anastomosis champions' will be asked to co-ordinate training days, an in-theatre pilot of the Safe-anastomosis checklist in their local centre, and encourage completion of the online

educational module by all members of the theatre team (e.g. local presentations to research and/or governance meetings).

All surgeons who perform (e.g. electively) or who are likely to perform right colectomy (e.g. whilst on call) will be invited to complete the online educational module. The training modules will be password protected to monitor compliance within the experimental arm, and centre-level completion rates monitored. Once the randomisation sequence requires implementation of the QII, this will be introduced over an implementation period of one month before 'post-implementation' data collection is commenced.

STANDARDISATION OF OTHER SURGICAL PROCESSES

As a pragmatic clinical study, other aspects of the operation, apart from those allocated as part of the education tool, will be determined by the preference of the attending surgeon and anaesthetist, and not be further defined within the *EAGLE Protocol*. Participating centres will be expected to implement the World Health Organisation Surgical Safety Checklist for all participants to standardise perioperative care prior to site opening; the implementation of individual components of this checklist will not be recorded for the purposes of the study. Within this pragmatic study, other anastomotic leak reduction measures may be used at the surgeon's discretion, for example indocyanine-green fluorescence assessment of bowel perfusion. These measures will not be controlled for within the study protocol.

PRIMARY OUTCOME MEASURE

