- During the index hospital admission.
- At 30 days after the operation.

Data will be entered directly onto the secure electronic EAGLE REDCap database by study collaborators at the participating hospital sites.

Site study collaborators will be provided with a paper copy of the eCRF to facilitate data collection. If this is used, they should then transfer data from the paper CRF into the online EAGLE database (https://www.bistc.redcap.bham.ac.uk). EAGLE data management staff will check all incoming data CRFs for completeness, data consistency and compliance with the protocol. If discrepancies or missing data are identified, the EAGLE data management staff will raise queries with the research team at the participating hospital via the EAGLE database.

Data Security and Data Protection

The security of the Study Database System is governed by the policies of the University of Birmingham. The EAGLE study database will be hosted on the REDCap system managed and maintained by the BiSTC.

Data management and data security within the BiSTC will abide by the requirements of the General Data Protection Regulations (GDPR) and any subsequent amendments. The study will be conducted at collaborating sites in accordance with the country-specific data protection requirements. Data will be acquired and stored on the REDCap platform. Access to data will be restricted by usernames and passwords, at participating sites. Each participant will be allocated a unique study number at entry. All communication will use this as the identifier. All data will be analysed and reported in summary format. No individual will be identifiable.

QUALITY CONTROL AND QUALITY ASSURANCE

Site set-up and site initiation

Study collaborators at participating hospitals will undergo a detailed, standardised site set-up training package. The package is formed of multiple components and covers the following areas:

Online training modules

This will include modules on the intervention, study set-up, study delivery, and follow-up. Study-specific GCP training will be incorporated throughout these modules.

Online site initiation visit

Once a site has completed all set-up process, all team site team members will be invited to attend a teleconference with an EAGLE Coordinator and/or Operations Committee member. This teleconference will cover details regarding the intervention, study delivery, and follow-up.

Ongoing support

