Each local principal investigator will have ongoing support from an assigned EAGLE Coordinator with at least weekly teleconference or email contact. As the study proceeds EAGLE Coordinators will tailor the content of these weekly contacts to the specific study processes that are relevant at that time.

All training has been CPD-accredited (3 points) by the Royal College of Surgeons of England.

Site training is mandatory and completion of each module by the relevant staff is a prerequisite to site opening to recruitment. The monitoring of completion of training will be undertaken by staff at the EAGLE Study Office.

Prior to opening, all participating local Principal Investigators will sign an Investigator's Agreement with the University of Birmingham to document acceptance of the responsibilities of the PI at the site.

Monitoring

Due to the nature of EAGLE, monitoring will be employed to ensure the credibility of the data. Monitoring will be undertaken centrally and will include, but will not be limited to, monitoring of: protocol adherence; patient selection and minimisation of selection bias; review of data relating to the primary and secondary outcomes. Monitoring will be via data validation and range checks built into the REDCap database used to collect and manage the data; statistical monitoring techniques will be used to compare data from different sites to identify sites that may warrant further investigation, site monitoring and/or support and training. Review by the study oversight committees (SSC, DMOC, SMG) will also include the review of completion of primary and secondary outcomes, adherence to protocol, and selection bias.

EAGLE study staff from UoB will be in regular contact with the site research teams to check on progress and address any queries that they may have.

The EAGLE Data Management Committee will check submitted CRFs from the participating hospitals for compliance with the protocol, data consistency and missing data. They will send participating hospitals data queries for missing data or clarification of inconsistencies or discrepancies.

Data validation

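### The protocol contradicts itself on early exposure: every site must complete set-up modules on the intervention before opening, yet no site is to be exposed before its allocated time

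*Protocol*

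**What the plan says.** **Set-up text (Quality Control and Quality Assurance).** Under Site set-up and site initiation: "Study collaborators at participating hospitals will undergo a detailed, standardised site set-up training package". Under Online training modules: "This will include modules on the intervention, study set-up, study delivery, and follow-up". Under Online site initiation visit, for a call to which the site team is invited once set-up is complete: "This teleconference will cover details regarding the intervention, study delivery, and follow-up". Under Ongoing support: "Site training is mandatory and completion of each module by the relevant staff is a prerequisite to site opening to recruitment". None of these paragraphs distinguishes between randomised sequences.

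**Timing text (Study Interventions and the champions section).** Under Intervention timing: "Sites will not be exposed to the study intervention before their allocated timing", and "this will be ensured by time-locked password access to QII materials". Training platform places completion of the educational module in the one-month implementation period. Safe-Anastomosis Champions and Training says: "Once the randomisation sequence requires implementation of the QII, this will be introduced over an implementation period of one month", before post-implementation data are collected.

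**Design text (Study Design, Figure 1 description).** Sequence 1 supplies data only after the intervention, sequence 2 before and after it, and sequence 3 only before it. The same section names staff already knowing about the intervention as a threat to baseline data, and aims to finish data collection within 12 months for that reason.

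**The concern.** The intervention is educational and behavioural: risk stratification, a checklist and harmonised technique. Telling staff what it contains is itself a form of exposure. For sequences 2 and 3, opening to recruitment means starting to collect control data, so a module that must be finished before opening comes before those data.

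If intervention content reaches these hospitals at that point, control practice may move towards intervention practice and the contrast shrinks. The intention-to-treat analysis cannot restore a lost contrast, and the sample size uses the full difference of 8.1% v 5.6% with no allowance for control-period exposure. Of the four cluster-periods in each matched triplet, two are control (the first period of sequence 2 and the only period of sequence 3). Control data are therefore planned for about 4,440 × 2/4 = 2,220 patients. That is the pool at risk, not a count of patients shown to be affected.

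**Working it through.** **Step 1. The two sets of instructions side by side**

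| Question | Set-up text | Timing text |
|---|---|---|
| When does intervention content reach a site? | Set-up modules before opening; the call once set-up is complete | Only at the allocated time, over one month |
| Which sequences? | All; no exception | Depends on sequence: after the control period for sequence 2, after data collection for sequence 3 |
| Who? | Study collaborators and relevant staff | All surgeons who perform or are likely to perform right colectomy are invited |
| Safeguard? | None stated | Time-locked passwords on the intervention materials |

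For sequence 1 the two columns need not conflict, because it collects no control data. For sequences 2 and 3 they cannot both be followed if the set-up modules carry intervention content. The document does not say whether those modules are the time-locked ones, a general overview, or something deferred for these sequences.

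**Step 2. Reproduce the planned size**

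Inputs from the Sample Size section: p₁ = 0.081, p₂ = 0.056, 80% power, 5% significance (taken as two-sided; the protocol does not say), ICC = 0.05 without decay, m = 10 patients per cluster-period, 14% inflation for unequal recruitment.

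- Individually randomised size: n per arm = [1.960·√(2p̄q̄) + 0.842·√(p₁q₁ + p₂q₂)]² / (p₁ − p₂)², with p̄ = 0.0685, gives 1,602, so N = 3,204.
- Variance of a cluster-period mean, in units of the outcome variance: v = [1 + (m − 1)·ICC]/m = 1.45/10 = 0.145.
- Correlation between two period means of one hospital: r = m·ICC/[1 + (m − 1)·ICC] = 0.5/1.45 = 0.345.
- Dog-leg variance of the effect with K hospitals: 3v(1 − r/2)/K = 3 × 0.145 × 0.8276/K = 0.36/K. Generalised least squares with three equal sequences, a fixed period effect and a random hospital effect gives the same value.
- Setting 0.36/K = 4/N gives K = 0.36 × 3,204/4 = 288.4, so 289 hospitals. Patients are 288.36 × 40/3 = 3,845, a design effect of 1.20.
- With 14% inflation: 329 hospitals and 4,383 patients.

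The protocol states 292 and 3,895, then 333 and 4,440. The difference is 1.3%, so the stated size is reproduced and its basis is clear.

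**Step 3. What contamination would cost, if it occurred**

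Take 333/1.14 = 292 equal-sized hospitals. The equivalent individually randomised size is 4 × 292/0.36 = 3,244, or n = 1,622 per arm. Let control patients already have a fraction f of the effect, so the control rate is 8.1% − f × 2.5 points. Then

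power = Φ{ [(p₁ − p₂)·√n − 1.960·√(2p̄q̄)] / √(p₁q₁ + p₂q₂) }.

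| f (assumed) | Control rate | Power | Hospitals for 80% power, with 14% inflation |
|---|---|---|---|
| 0 | 8.1% | 80.5% | 329 |
| 10% | 7.85% | 72.5% | 399 |
| 25% | 7.475% | 57.9% | 560 |
| 50% | 6.85% | 31.3% | 1,204 |

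None of the values of f comes from the document.

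**The case against.** A reader might infer that sequence 2 and 3 hospitals are in fact exposed, that the effect is diluted, and that every control patient is affected. The document does not support that, for these reasons:

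- **Two training streams.** The intervention is taught through the password-protected Educational Module in the implementation month. The set-up package is described separately and is for study collaborators. Surgeons are only invited to take the educational module, a planned subgroup allows for hospitals where fewer than 50% of surgeons complete it, and the case report form asks Yes/No whether the senior surgeon has done so. A module of that kind does not look like a mandatory pre-opening one. The set-up item may be no more than an outline of what is being tested.
- **Limited reach.** Only relevant staff must complete the modules, the call is by invitation, and the Authorship section normally allows seven collaborators per hospital. Nothing says that every surgeon operating on control patients takes the package.
- **A stated safeguard.** A specific time-lock exists, and nothing in the text shows that it fails.
- **Arbitrary fractions.** Half the effect of a three-part programme gained from an undefined set-up item would be extreme.

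These points remove any claim of established contamination. They do not remove the contradiction. The time-lock is stated for password access to intervention materials; the protocol does not say that it covers the set-up modules or the call. The call covers details of the intervention, not merely its existence. The collaborators include the consultant surgeon leading the site and, usually, a surgical trainee, an anaesthetist and a theatre nurse acting as champions, who later spread the programme locally. The statement under Ongoing support that all training is CPD-accredited leaves the boundary between the two streams unclear.

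**Conclusion.** The contradiction is real and must be reconciled. The set-up text requires modules on the intervention before any site opens, with no exception by sequence; the timing text says no site is exposed early. Following the set-up text as written would give intervention content to key staff at sequence 2 and 3 hospitals before or during their control period, which is the kind of contamination the Study Design section sets out to prevent.

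The consequence is conditional. Any bias would be expected to run towards no effect, but neither its presence nor its size can be derived from the protocol. The fall in power from about 81% to about 73%, 58% or 31% rests on assumed fractions of 10%, 25% and 50%, on those fractions applying on average to all control patients, and on the protocol's own ICC, cluster-period size and event rates. It shows what is at stake, not what will happen. Contaminated control data could not be repaired afterwards, so the text should be settled before sites open.

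**What to change.** 1. Limit the pre-opening prerequisite and the initiation call, for all sites, to study set-up, eligibility, outcome definitions, data entry and follow-up.
2. Place every module and call item with intervention content behind the time-lock already described under Intervention timing. Release it at the hospital's scheduled implementation month, which for sequence 3 falls after data collection.
3. Reword Intervention timing, Safe-Anastomosis Champions and Training, Site set-up and site initiation, and Ongoing support so that they agree on what is given before opening, to whom, and what stays locked.

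The cost is protocol wording, re-ordering of existing online modules, and a second short call for sequences 2 and 3. The change would not remove all prior knowledge: the protocol prints the checklist, and the case report form asks about the checklist, the risk calculation and the module.
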